6.5.3. Site Discontinuation

The Sponsor has the right to terminate the study or terminate enrollment and remove all appropriate study materials from the study site for the following reasons:

1. It becomes apparent that patient enrollment is unsatisfactory as to quality (violations of inclusion or exclusion criteria) or enrollment rate;
2. The completion of the CRFs is inaccurate, incomplete or considerably delinquent; and
3. There are repeated, uncorrected protocol violations.

All patients treated with the study device before the Site discontinuation will be followed according to the study protocol.

6.5.4. Source Data

Source documents are original documents, data, and records from which participants' CRF data are obtained. These include, but are not limited to, hospital records (from which medical history and previous and concurrent medication may be summarized into the CRF), clinical and office charts, laboratory and pharmacy records, diaries, microfiches, radiographs, and correspondence. All documents are stored safely in confidential conditions at the study site.

7. TREATMENT OF TRIAL PARTICIPANTS

7.1. Description of Study Intervention(s)

Description of the device and of study intervention(s) is reported in the Investigator Brochure.

The physician may decide that cementoplasty (i.e., Vertebroplasty or Kyphoplasty) is required after the ablation procedure. This information will be collected during the procedure and during any subsequent follow-up procedures.

In the treatment of metastases involving weight-bearing bones – such as the spine or acetabulum – cement is routinely instilled after RFA into the ablation cavity for stabilization or prevention of pathologic fractures [Wallace 2015]. Even when a gross pathologic fracture is not evident, cementoplasty may contribute to pain relief by stabilizing trabecular microfractures [Heran 2006]. The exothermic reaction from polymethyl methacrylate polymerization is also thought to cause destruction of pain fibers at the margins of the ablation zone [Lane 2001, Weill 1996]. Because the risk of cementoplasty is low, it is routinely performed after ablation at many institutions [Wallace 2015, Wallace 2016, Anchala 2014, Hillen 2014]. The risk of symptomatic extravasation may be reduced through the use of ultrahigh viscosity cement [Wallace 2016].

7.2. Maintenance and storage of device

Maintenance and storage of the device are described in dedicated sections of Investigator Brochure and Instruction for Use.

7.3. Concomitant Medication

There are no restrictions to prior or concomitant medications before or during the study. The specific concomitant medications listed below should be documented as concomitant medications and will be updated at each visit:

- Osteoporosis medication(s): antiresorptive medications (e.g., bisphosphonates, parathyroid hormone (PTH), calcitonin), calcium, and vitamin D.
- Steroid(s): any steroid use, including steroid inhalers
- Oral narcotics in the last 24 hours. This information will be converted to oral morphine equivalent dose (OMED) (including transdermal patches)

8. SAFETY REPORTING

8.1. Definitions

8.1.1. Adverse Event (AE)

An adverse event is defined in ISO 14155:2020 as any untoward medical occurrence, unintended disease or injury, or untoward clinical signs (including abnormal laboratory findings) in subjects, users or other persons, whether or not related to the investigational medical device and whether anticipated or unanticipated.

All adverse events, regardless of severity, associated with the use of the SPINERY device will be reported on the adverse event CRF.

8.1.2. Adverse Device Effect (ADE)

An adverse device effect is defined in ISO 14155:2020 as an adverse event related to the use of an investigational medical device.

This definition includes adverse events resulting from insufficient or inadequate instructions for use, deployment, implantation, installation, or operation, or any malfunction of the investigational medical device.

8.1.3. Unanticipated Adverse Device Effect (UADE)

An Unanticipated Adverse Device Effect (UADE) is defined as any serious adverse effect on health or safety, or any life-threatening problem caused by, or associated with, the SPINERY device, the effect of which was not previously identified in nature, severity or degree of incidence in the study protocol or any other unanticipated serious problem associated with the study device that relates to the rights, safety or welfare of subjects.

In the event of an unanticipated adverse device effect, the Investigator and/or other professional personnel in attendance will undertake whatever therapy is indicated. If an unanticipated adverse device effect occurs, the Investigator will submit a report to Sponsor and the IRB as soon as possible but no later than ten (10) working days (or as indicated by applicable regulations) after the Investigator learns of the event. The nature and causes of the problem will be reported and any treatment that is administered due to the event will be described in detail. This information will be reported on the Adverse Event CRF and documents from the medical records will be provided to the Sponsor.

It is the responsibility of the Sponsor/Manufacturer to conduct an evaluation (including discussions with the Investigator) of the event and, with respect to the applicable regulations, to determine if it is an unanticipated adverse device effect. If the event is an unanticipated adverse device effect, the Sponsor must notify all participating Investigators and the reviewing IRB within ten (10) working days (or as indicated by applicable regulations) of receiving notification of occurrence of the event.

If the Sponsor determines that an adverse device effect presents an unreasonable risk to the patient population, study enrollment shall be terminated. Termination will occur no later than five (5) working days after the determination is made and no later than 15 working days after the initial notification by the Investigator. A terminated investigation will not resume without approval from the local Competent Authority and the IRB.

8.1.4. Serious Adverse Event (SAE)

A serious adverse event (SAE) is defined in ISO 14155:2020 as an adverse event that led to any of the following:

- a) led to death,
- b) led to serious deterioration in the health of the subject, that either resulted in
 - 1) a life-threatening illness or injury, or
 - 2) a permanent impairment of a body structure or a body function, or
 - 3) in-patient or prolonged hospitalization, or
 - 4) medical or surgical intervention to prevent life-threatening illness or injury or permanent impairment to a body structure or a body function,
 - 5) chronic disease
- c) led to fetal distress, fetal death or a congenital abnormality or birth defect including physical or mental impairment

Planned hospitalization for a pre-existing condition, or a procedure required by the CIP, without serious deterioration in health, is not considered a serious adverse event.

To ensure no confusion or misunderstanding of the difference between the terms "serious" and "severe", which are not synonymous, the following note of clarification is provided:

The term "severe" is often used to describe the intensity (severity) of a specific event (as in mild, moderate, or severe myocardial infarction); the event itself, however, may be of relatively minor medical significance (such as severe headache). This is not the same as "serious," which is based on patient/event outcome or action criteria usually associated with events that pose a threat to a participant's life or functioning. Seriousness (not severity) serves as a guide for defining regulatory reporting obligations.

8.1.5. Serious Adverse Device Effects (SADE)

A serious adverse device effect (SADE) is defined in ISO 14155:2020 as an adverse device effect that has resulted in any of the consequences characteristic of a serious adverse event.

8.1.6. Unanticipated Serious Adverse Device Effect (USADE)

An unanticipated serious adverse device effect (USADE) is an effect which by its nature, incidence, severity or outcome has not been identified in the current version of the risk analysis report.

Note: Anticipated serious adverse device effect (ASADE) is an effect which by its nature, incidence, severity or outcome has been identified in the risk analysis report.

8.1.7. Device Deficiency and Malfunction

Device deficiency and malfunction information will be collected throughout the study. Device deficiencies (event, date of onset, severity, duration, and relationship) will be recorded on the applicable CRFs.

A device deficiency is defined in ISO 14155:2020 as an inadequacy of a medical device with respect to its identity, quality, durability, reliability, usability, safety or performance.

A device malfunction is a failure of the investigational medical device to perform in accordance with its intended purpose when used in accordance with the instructions for use or CIP, or IB.

8.2. Reporting procedures

8.2.1. Reporting of an AE

All AE(s) and ADE(s) occurring during the study observed by the investigator or reported by the participant, whether or not attributed to the device under investigation are recorded on the CRF as specified in the protocol.

The following information should be recorded: description, date of onset and end date, severity, assessment of relatedness to device, other suspect drug or device and action taken. Follow-up information should be provided as necessary.

The relationship of AEs to the device is assessed by a medically qualified investigator or by the sponsor/manufacturer and is to be followed up until resolution or the event is considered stable.

All ADE(s) that result in a participant's withdrawal from the study or are present at the end of the study, should be followed up until a satisfactory resolution occurs.

Where relevant, any pregnancy occurring during the clinical study and the outcome of the pregnancy, should be recorded and followed up for congenital abnormality or birth defect.

8.2.2. Reporting of a SAEs/ SADEs/ UADEs

All SAE/SADE/UADEs must be reported to the study Sponsor Axon as soon as possible and no later than 2 days after the Investigator first learns of the event.

Adverse events will be recorded on the applicable CRFs (event, date of onset, severity, duration, relationship to device and procedure) by the Investigator or designee and will be followed until they are adequately resolved or explained.

Notification of adverse events to Axon may be completed via telephone, fax, email, or through the electronic database (EDC). Reportable adverse events will be submitted to the applicable EC and regulatory authorities per national and local reporting regulations and requirements and timeframes. Adverse event reporting must comply with national regulations of each European Country where the investigation is conducted. Axon will comply with any specific country requirements regarding adverse event reporting.

The Sponsor will report SAEs to the Competent Authorities as applicable according to national regulations MDCG 2020-10/1. Reporting will include report table, quarterly SAE summary reports, and any applicable national formats for reporting individual SAEs as applicable.

The Principal Investigator is required to report all Device-Related, Procedure-Related and Serious Adverse Events to the Sponsor. Adverse events will be recorded on the Adverse Event CRF and may or may not be device or operative site related. Adverse events that are associated with the procedure are included in the paragraph 8.2.3 and defined in the Guidelines for clinical investigation ISO14155:2020. All adverse events, regardless of severity, associated with the use of the SPINERY device will be reported on the adverse event CRFs.

The contact information for Axon is below:

Axon srl

[name]

[name]

Italy.

[name]

Email: [contact]

[contact]

8.2.3. Specific Adverse Device Effect (ADE)

The following ADE should be carefully assessed as they are recognized as possible ADE for SPINERY based on the state of the art of other medical devices:

- Carbonization
- Post-operative pain
- Limited/uncomplete treatment due to anatomical peculiarities
- Damage to surrounding tissue through iatrogenic injury
- Nerve injury including thermal injury, puncture of spinal cord or nerve roots potentially resulting in radiculopathy, paresis, and paralysis
- Pulmonary embolism
- Hemothorax or pneumothorax
- Infection
- Unintended puncture
- Hemorrhage
- Hematoma

Unanticipated adverse device effects can occur. If they do occur, they will be handled as discussed in paragraph 8.1.3.

Aside from the risks listed above, there are no known gender-specific risks associated with the use of the SPINERY device. Minimization of the risks will be accomplished by selection of patients who are appropriate candidates for this device and by careful selection of Investigators and centers that have appropriate experience with this type of procedure. Also, intervention techniques, peri-interventional and post-interventional, will be those that are typically used in each study center.

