Objective(s), primary and secondary	
Primary objectives:
 
 1. To demonstrate that SPINERY RF device is effective in short-term (3 months) pain reduction in patients affected by metastatic bone tumors involving the vertebral bodies, sacrum, iliac crest and peri-acetabulum with indication for standard therapy and in patients who have failed, not candidates or refuse standard therapy; 2. To demonstrate that SPINERY RF device is safe in the RF ablation treatment of metastatic bone tumors, without causing device-related adverse events including, in particular, nerve injury; 
Secondary objectives:
 
 1. To demonstrate that SPINERY RF device is effective in long-term (up to 12 months) pain reduction in patients affected by metastatic bone tumors in the areas of vertebral bodies (thoracic and/or lumbar), sacrum, iliac crest and peri-acetabulum; 2. To demonstrate safety in relation to usability; 3. To demonstrate the procedural performance in terms of a short learning curve.
Hypotheses, primary and secondary	
Primary hypothesis:
 
 - BPI Brief Pain Inventory scale performance in terms of palliative treatment: 
H0: $\mu_c = 0$
 
HA: $\mu_c \neq 0$
 
Where μ_c is the mean change from baseline to the 3-month visit in worst-pain score.
 
No formal hypotheses for the remaining objectives.

Risks and anticipated adverse device effects to be assessed	Risks of innovative device SPINERY are the same of the state-of-the-art technology: 
 - Carbonization - Post-operative pain

	
 - Limited/uncomplete treatment due to anatomical peculiarities - damage to surrounding tissue through iatrogenic injury - Nerve injury including thermal injury, puncture of spinal cord or nerve roots potentially resulting in radiculopathy, paresis, and paralysis - Pulmonary embolism - Hemothorax or pneumothorax - Infection - Unintended puncture - Hemorrhage - Hematoma
Design of the clinical investigation	
Clinical development stage	
Pivotal confirmatory.
 
Justification: pre-market study for demonstration of conformity of the device with the Essential Requirements for CE-marking.

Design type	Prospective, Single arm, Multicenter
Control group	No control group

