5. ENDPOINTS

5.1. Primary Endpoints

The primary endpoints of the study are:

- Change of Worst Pain Score expressed as average reduction of 2 BPI (Brief Pain Inventory) scores: Thoracic/Lumbar/ Peri-acetabulum/Iliac Crest/Sacrum RF Ablation [Time Frame: Baseline vs. 3 months];

Change in pain will be calculated as:

$$\mu c = \text{worst-pain 3-month} - \text{worst-pain baseline}$$

A negative average value for change in pain represents a lowering of the subject's pain score (an improvement, or reduction in pain) and a positive value represents an increase in the subject's pain score (a worsening or increase in pain)

Worst pain score at the target treatment site will be collected from the BPI in the past 24 hours.

- Completion (%) of the ablation procedure without device-related adverse events including in particular nerve injury [Timeframe: Post-procedure, 3 months].

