Postoperative	Primary safety endpoint	Number of device-related adverse events observed
1 month	First secondary endpoint at the first timeframe (1 month)	Data on change of worst pain score after 1 month from the procedure
3 months	Primary efficacy endpoint	Data on change of worst pain score after 3 months from the procedure
12 months - Final Clinical Report	First secondary endpoint at the second timeframe (12 months)	Data on change of worst pain score after 12 months from the procedure

Table 2 - Clinical Report Plan

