6.3.1. Inclusion criteria

Participants are eligible to enroll in the study only if *all* the following criteria apply:

1. Patients with painful metastatic malignant lesions involving bone;
2. Patients, candidates to standard therapy, in which the RF ablation can be performed in combination with the Standard Therapy in accordance with the Investigator's indications;
3. Patients who have failed, not candidates or refuse Standard Therapy (chemotherapy or radiotherapy);
4. Patients with metastatic tumor size compatible with the expected ablation dimensions as reported for SPINERY devices in the IFU;
5. Patients with localized pain resulting from not more than two sites of symptomatic metastatic disease;
6. Patients that do not have evidence of impending fracture;
7. Patients with metastatic lesions targeted for treatment located in the thoracic and/or lumbar vertebral body(ies), peri-acetabulum, iliac crest, and/or sacrum - no restrictions on location of lesion;
8. Patients with BPI-Report worst pain score $\geq 4/10$ at the target treatment site within the past 24 hours;
9. Patients with Karnofsky score ≥ 40 at enrollment;
10. Patients willing and able to provide a signed and dated informed consent, comply with the study plan, follow up visits and phone calls;
11. Patients at least 18 years old at the time of informed consent.

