The EQ-5D descriptive system consists of 5 dimensions: mobility, self-care, usual activities, pain/discomfort, and anxiety/depression. Each dimension has 5 levels of severity: no problems, slight problems, moderate problems, severe problems and extreme problems. The subjects are asked to indicate their health status by selecting the most appropriate statement in each of the 5 dimensions.

The EQ VAS records the respondent's self-rated health on a 20 cm vertical, visual analogue scale with endpoints labelled as 'the best health you can imagine' and 'the worst health you can imagine'. This information can be used as a quantitative measure of health as judged by the individual respondents.

The EQ-5D can be completed by the subject, in-person interview, or by phone interview by the Principal Investigator or qualified (delegated) designee.

Adverse Events Assessment

Any adverse event meeting the definition of device, therapy and/or procedure related, as well as all device deficiencies that occur from enrollment through subject discontinuation from the study will be collected.

All device, therapy and/or procedure-related adverse events will be collected for this study from enrollment to the end of the study, including events related to:

- The device components and/or procedure (Bone Access Kit, Probe, generator, etc.)
- Surgery or anesthesia regarding the initial or repeat procedure

Any adverse event due to the device, detected during the ablation procedure and/or during follow-up, will be recorded and evaluated through a dedicated case report form. The case report form will include at least the following information: date of the event, diagnosis or description of the event, severity assessment, treatment, outcome and date of resolution. The investigator is responsible for the detailed recording of the adverse event through the dedicated case report form and for the communication of the adverse event to the Sponsor.

The clinical course of each adverse event will be followed by the physician until resolution or until the subject's participation in the study is discontinued.

Deviations

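### A fracture of the treated bone that is attributed to the metastasis leaves the primary safety percentage unchanged, and sections 6.4.4 and 8.2.1 disagree on whether it is recorded

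*Combined protocol and SAP*

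**What the plan says.** - **Fracture as something to prevent.** Section 7.1 says that in weight-bearing bone such as the spine or acetabulum "cement is routinely instilled after RFA into the ablation cavity for stabilization or prevention of pathologic fractures". Cementoplasty is left to the physician, and of its use the section says: "This information will be collected during the procedure and during any subsequent follow-up procedures".
- **Entry.** Inclusion criterion 6 (section 6.3.1) reads "Patients that do not have evidence of impending fracture".
- **Risk lists.** The synopsis states "Risks of innovative device SPINERY are the same of the state-of-the-art technology" and lists 11 effects. Section 8.2.3 gives the same 11, introduced by "The following ADE should be carefully assessed as they are recognized as possible ADE for SPINERY based on the state of the art". Neither names fracture.
- **Primary safety endpoint.** Section 5.1: "Completion (%) of the ablation procedure without device-related adverse events including in particular nerve injury", assessed post-procedure and at 3 months. No threshold is set.
- **Reporting.** Table 2 (section 6.1) gives the safety content as "Number of device-related adverse events observed", in the postoperative report only. Its 1-, 3- and 12-month rows list worst pain, and section 10.4 plans statistical analysis of the BPI worst pain score.
- **Collection.** Section 6.4.4 collects "Any adverse event meeting the definition of device, therapy and/or procedure related", plus device deficiencies. Section 8.2.1 instead requires every adverse event on the CRF, attributed to the device or not.
- **Attribution.** Under section 8.2.1 a medically qualified investigator or the sponsor/manufacturer judges relatedness. No criteria and no adjudication are described.

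**The concern.** Section 2 names pathologic fracture among the consequences of bone metastases, so disease is always an available explanation when a treated bone fractures. Once that label is given, the event fails the device-related condition and drops out of the primary safety percentage. With a single arm there is no control rate against which to test the label.

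The trial is the pivotal study for CE marking, and its second primary objective is to show that ablation with the device is safe. A reader of the headline percentage could not tell whether no treated bone fractured, or several did and all were attributed to the cancer. Only a count made regardless of attribution, with the attribution shown beside it, answers that question.

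**Working it through.** **1. The plan's own figures.** Section 10.2 states 36 evaluable and 52 enrolled patients, for pain only; no sample size or precision is given for safety. From a difference of 2 points, SD 3, correlation 0.3, two-sided alpha 0.05 and power 0.90:

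- SD of change = 3 × √(2 × (1 − 0.3)) = 3.55.
- Paired t-test power (noncentral t) is 0.899 at n = 35 and 0.908 at n = 36, so 36 is reproduced.
- 36 / (1 − 0.30) = 51.4, rounded up to 52.

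**2. Path of a treated-site fracture attributed to the metastasis.**

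| Place | Rule | Outcome |
|---|---|---|
| 6.4.4 | Device-, therapy- or procedure-related events | May not be collected |
| 8.2.1 | All adverse events | On the CRF |
| 8.2.2 | All serious events go to the sponsor | Reaches the sponsor if serious |
| 5.1 | Device-related events only | Not counted |
| Table 2 | Device-related events only | Not in the named content |
| 10.4 | BPI worst pain only | No analysis planned |

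The first two rows contradict each other. The last three agree, and they produce the gap in the safety result.

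**3. Size, as an illustration.** The documents give no fracture rate, so the number k of patients with such a fracture is an assumption. Assume no other failures. The endpoint as written then reads n/n whatever k is. Counting the fractures as failures gives (n − k)/n. The exact (Clopper-Pearson) 95% limits are the 0.025 quantile of Beta(n − k, k + 1) and, for k > 0, the 0.975 quantile of Beta(n − k + 1, k).

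| k | All 52 followed | 36 followed |
|---|---|---|
| 0 | 100% (93.2 to 100) | 100% (90.3 to 100) |
| 1 | 98.1% (89.7 to 100.0) | 97.2% (85.5 to 99.9) |
| 3 | 94.2% (84.1 to 98.8) | 91.7% (77.5 to 98.2) |
| 5 | 90.4% (79.0 to 96.8) | 86.1% (70.5 to 95.3) |

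One patient is 1/52 = 1.9 points, or 1/36 = 2.8 points. The second column is shown because section 10.2 expects about 30% attrition by 3 months.

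**4. Would any fracture be expected?** For assumed true rates of 2%, 5% and 10%, the expected number in 52 patients is 1.0, 2.6 and 5.2. The chance of at least one, 1 − (1 − p)^52, is 65%, 93% and 99.6%.

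**The case against.** A sponsor could fairly answer that the safety system is wider than the endpoint. Section 8.2.1 records all adverse events. Section 8.2.2 sends every serious event to the sponsor within 2 days and provides quarterly summaries of serious events. Section 6.5.1 describes an independent DSMB. Section 6.1 expects each study report to consider safety and clinical events. All of this stands, and it rules out several stronger readings that a reader might infer:

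- **That such a fracture vanishes, or must be reported as zero.** Only the primary percentage and the named Table 2 content are blind to it. Non-collection follows only from section 6.4.4, which section 8.2.1 contradicts.
- **That the protocol names fracture as a harm of ablation.** Section 7.1 speaks of preventing pathologic fracture in metastatic weight-bearing bone. It does not say that ablation causes fracture or raises its risk.
- **That any fracture seen after Day 0 is new.** Criterion 6 excludes impending fracture. Existing fracture is excluded only in part, by criterion 19 for prostatic or other osteoblastic spinal metastases. Neither visit schedule has a baseline fracture assessment.
- **That the omission from section 8.2.3 causes the loss.** That section allows for unanticipated effects, and a fracture judged device-related would count although unlisted. Adding it to the list would not cure the problem, and it could change whether a serious device-caused fracture is handled as unanticipated under section 8.1.3.
- **That later cementoplasty is itself a safety failure.** It is discretionary and may be preventive.

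What remains is that no planned output is certain to show treated-site fractures regardless of attribution, and that the collection rules conflict.

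**Conclusion.** The point holds for the planned safety result, not for every record. A treated-site fracture attributed to disease does not move the primary safety percentage, the attribution has no stated criteria and no control group to check it, and sections 6.4.4 and 8.2.1 give incompatible collection rules.

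The size is unknown. The figures above assume that every such fracture is attributed to disease and that no other device-related event occurs; the 52-patient column also assumes complete follow-up. On that basis each fracture is worth 1.9 points, or 2.8 points with 36 followed. The sample size is unaffected. This is a worthwhile and inexpensive improvement to a pivotal safety report, not a defect that invalidates the trial.

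**What to change.** 1. Reconcile section 6.4.4 with section 8.2.1 so that fracture or collapse of the treated bone is recorded on the existing adverse event CRF whatever its attribution.
2. In the 3- and 12-month reports, give the number and proportion of treated patients with a new or worsened fracture at the treated bone, with the exact 95% CI, the number followed and the attribution of each event. Place this beside the primary safety percentage, whose definition stays as it is.
3. Add a sensitivity version of that percentage in which these fractures count as failures.
4. Describe later cementoplasty or stabilization at the treated bone separately, without counting it as a failure.

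The cost is a wording change and one table from forms already in use, with no added visits, imaging or patients, and the clinical handling of cementoplasty is untouched. The reported safety figure may look slightly less favourable, and some counted fractures will be due to the disease, which is why attribution is shown. Without scheduled imaging, silent fractures may be missed and fractures already present at baseline may be misclassified; the report should say so.
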